### Study Synopsis

This study will include adult outpatients 18-65 years of age with major depressive disorder (MDD) with subjective reporting of cognitive dysfunction treated with flexible-dose vortioxetine (5-20 mg/day) for eight weeks. Following completion of the informed consent process, this study will consist of a screening period (visit 1) of 2-14 days to assess inclusion/exclusion criteria. Subjects who continue to meet inclusion criteria at baseline (visit 2) will begin the assessment and treatment phase of the study.

The first EEG/BNA (BNA) will be performed at the screen visit. Subsequent BNA will be at baseline, 2-weeks after the start of treatment, and at the end of 8 weeks of treatment (or early termination).

The Schedule of Events (Appendix I) shows detailed study procedures that will be performed at each visit. The table below clarifies the schedule of dosing and attendant BNA tests.

### Quick Summary of Study Visits, Dosing and BNA

Visit #	Screen 1	Baseline 2	3	4	5	6	7	8	9	10 (or ET)
Day	-2 to -14	0	7	14	21	28	35	42	49	56
Treatment Week	-1	0	1	2	3	4	5	6	7	8
Dose mg/day		10	5-10	5-10	5-20	5-20	5-20	5-20*	5-20*	5-20
BNA test	BNA	BNA		BNA						BNA

\*No dose changes allowed after visit 8

### Subject Population:

Subjects aged 18 to 65 years old with acute single episode, acute recurrent MDD and acute recurrent MDD with incomplete inter-episode recovery who report subjective cognitive dysfunction (such as difficulty concentrating, slow thinking, and difficulty in learning new things or remembering things) that correlated with the timing of their current major depressive episode (MDE).

### Number of Subjects:

40 subjects enrolled. For purposes of IRB reporting, an enrolled subject is one who signs informed consent. For purposes of data analysis and reporting to the funding organization, an enrolled subject is one who meets all inclusion criteria and no exclusion criteria and completes the baseline visit including the baseline BNA.

### Number of Sites: (U.S. Study)

2: Chicago, IL and Skokie, IL

### Dose Level(s):

5 mg/d, 10mg/d, 15 mg/d, 20mg/d. Route of Administration: Oral

### Duration of Vortioxetine Treatment:

One dose daily for 8 weeks.

### Period of Evaluation:

Screening phase 1-2 weeks; treatment phase 8 weeks.

**Introduction:**

Major depressive disorder (MDD) is the most common psychiatric disorder with a lifetime prevalence of 16.2% and a 12-month prevalence of 6.6% in developed countries [1]. It represents one of the most serious challenges faced by healthcare providers throughout the world, being a leading cause of disability globally [2] [3]. MDD is characterized by the presence of 1 or more MDEs that presents with depressed mood, loss of interest or pleasure, disturbed sleep or appetite, low energy, and feelings of guilt or low self-worth [4].

It is well established that mood disorders are also associated with cognitive dysfunction [5,6]. In fact, growing evidence from neuropsychological studies suggests that the majority of patients suffering from MDD present with some form of dysfunction in certain cognitive domains (such as executive function [7-10], visuospatial short-term memory and learning and on verbal learning [11]; psychomotor speed and in immediate and delayed free recall [12] and working memory [13]) before treatment and are among the most common residual symptom domains after apparent successful treatment of other core MDD symptoms. Patients with depression also seem to perform significantly worse than normal controls on effort-demanding tasks, while they did not differ on the effortless tasks [14,15]. A study by Burt [16] showed that patients with depression performed approximately one half of a standard deviation worse than healthy subjects on verbal learning and memory tests. Other studies, however, found non-significant or only minimal differences in neuropsychological tests among patients with MDD and normal controls [17-19].

Regarding prevalence of cognitive dysfunction in MDD patients, little is still known. Afridi et al. [20], assessed cognitive disturbances among newly diagnosed depressed (n=30) and healthy subjects (n=30). He found that 63.3% of the depressed patients had cognitive difficulties compared to 3.3% of healthy-controls, with attention/concentration being the most common domain of cognition affected, followed by memory disturbance. The presence or absence of cognitive dysfunction in MDD patients depends on a number of factors including symptom severity [21], presence of melancholic features [22], presence of recurrent episodes [23], presence of psychotic features [24], remitted versus acute states [25], age [26], and pharmacological and non-pharmacological interventions [27]. Regarding pharmacological interventions, some evidence shows that conventional antidepressants may worsen cognitive function (e.g., tricyclic antidepressants (TCAs) secondary to anticholinergic or antihistaminic effects; selective serotonin reuptake inhibitors (SSRIs) secondary to selective increase of serotonin (5-HT) resulting in diminished norepinephrine (NE) and dopamine (DA) output; mirtazapine secondary to antihistaminic effects [30].

Cognitive dysfunction in MDD may be a symptom of depressive illness and persist, as residual symptoms, despite otherwise effective antidepressant therapy [34]. As discussed above, they may also, however, emerge as adverse effects of some psychotropic medications, including antidepressants [26].

Various neurotransmitters are implicated in cognitive processes, including 5-HT, DA, NE, acetylcholine and histamine. Regarding 5-HT, it is known that 5-HT1A receptor agonists have shown differential effects on memory and executive function in healthy and psychiatrically ill populations [35]. In animal studies, 5-HT2A receptor agonists enhance associative learning and certain antagonists impair associative learning [36]. In addition, depletion of 5-HT has been shown to impair discrimination reversal performance, a form of cognitive flexibility [37]. Dopamine is also involved in cognitive flexibility, with a role in attentional selection, reversal and extinction learning [38], [39]. Animal studies have shown that blockade of DA receptors in the prefrontal

cortex impairs spatial working memory [39]. Norepinephrine appears to play a role in spatial working memory formation [38] as well as attentional set-shifting [37,38]. Acetylcholine has been implicated in aspects of reversal learning in the orbitofrontal cortex [37]. Furthermore, behavioral studies in humans suggest that acetylcholine is responsible for maintenance of attention and increased levels of this neurotransmitter are related to attentional effort [40]. Finally, histamine seems to affect learning and memory, partly via modulating acetylcholine release [41]. In rats, blockade of 113 receptors improves social memory, enhances attention and improves cognitive performance. Cetirizine, an H1 receptor antagonist, impairs memory processing speed [42; data on file with Takeda].

Vortioxetine is a novel antidepressant with hypothetical multimodal mechanism of action. It is thought to work through a combination of multiple pharmacological modes of action: 5-HT reuptake inhibition, 5-HT3 and 5-HT7 receptor antagonism, 5-HT1A receptor agonism, and 5-HT1B receptor partial agonism [43]. In vivo nonclinical studies have demonstrated that vortioxetine enhances levels of the neurotransmitters 5-HT, NE, DA, acetylcholine and histamine in specific areas of the brain [43]. These affinities are all considered to be of clinical relevance and involved in the mechanism of action at therapeutic doses.

Vortioxetine showed antidepressant activity in completed MDD studies in which primary endpoints were change in depressive symptoms. Currently, three placebo-controlled clinical trials demonstrate vortioxetine's efficacy on cognitive performance in adult outpatients with MDD (Katona, et al., 2012; McIntyre, et al., 2013; data on file with Takeda). Two of the above studies (Katona, McIntyre) included duloxetine as a comparator antidepressant; both active antidepressants demonstrated antidepressant efficacy compared to placebo. Vortioxetine, not duloxetine, showed improvement compared to placebo on the Digit Symbol Substitution Test (DSST). Results of these two studies also suggested that the improvement with vortioxetine (and not duloxetine) was a result of direct effects versus indirect (via mood) improvement in cognition. Correlating the clinical changes in mood and cognition with translational imaging data could provide insight to diagnose and manage cognitive changes associated with MDD.

Vortioxetine improved cognition sub-items in the Montgomery-Åsberg Depression Rating Scale (MADRS) [44] (Item 6 — concentration difficulties) [45] and Hamilton Anxiety Scale (HAM-A) [46] (Item 5 - concentration and memory) [47] when compared to placebo (in the trials in which the primary endpoint was also positive). In addition, exploratory cognitive tests for verbal learning (RAVLT — Rey Auditory Verbal Learning Test) [48] and executive function, working memory, processing speed and visuospatial attention DSST [49]) were included in a vortioxetine conducted study in elderly patients [50] with MDD (primary endpoint was change in depressive symptoms). In this study, vortioxetine 5 mg/day improved cognitive dysfunction in both tests whereas duloxetine (active reference) improved cognitive dysfunction in the RAVLT but not in the DSST. This finding is consistent with the literature as shown by a study in which elderly patients receiving duloxetine demonstrated significantly greater improvement in a composite cognitive score mainly driven by improved verbal learning and memory [51].

#### **Brain Network Activation:**

Appropriate diagnosis and differential diagnosis is critical to finding a treatment that will provide optimal efficacy. Currently, diagnosis depends on an assumption that historical and current clinical information is accurate and reliable. The need to find biomarkers to improve current diagnosis and differential diagnosis, and the potential to predict treatment outcome, remains a significant unmet need in the optimal management of MDD.

In recent years more attention has been devoted to the use of functional magnetic resonance imaging (fMRI) to assess the state of the frontolimbic circuit to diagnose depression and monitor response to treatment. In particular the activity of the rostral anterior cingulate cortex (rACC) measured both on fMRI and EEG has been demonstrated to be a reliable biomarker of depression and its response to antidepressant therapy.

Sensory evoked potentials (SEPs) are electrical potentials, recorded from the central nervous system of humans or animals (usually via EEG) while stimulating sense organs. They are distinct from spontaneous potentials (background EEG), which are recorded without stimulation. Contrary to spontaneous potentials, SEPs are phase-locked to the stimulus.

Event Related Potentials (ERPs) are msec by msec reflections of the direct macroscopic neural mass electrical activity of cell assemblies located in specific regions of the brain, during sensory, motor, and cognitive tasks. They are extracted from the background electroencephalogram (EEG) through a process of time-locked averaging process of many trials of the same type to the onset of a sensory stimulus or a motor response. As such, they offer a powerful technique for the noninvasive characterization of human brain function by means of identifying the timing, order of activation, and dynamic orchestration of brain regions during the unfolding of cognitive tasks.

Although Positron Emission Tomography (PET) and fMRI allow for precise localization of functional activations during cognitive tasks, their temporal resolution is limited by the slow time course of the hemodynamic response that they are reflecting (peaking 5 sec after an event and subsiding after 12-15 sec, and affecting both blocked and event-related fMRI designs). Because of the slowness of the hemodynamic response PET and conventional fMRI have limited temporal resolution, while ERPs allow selective averaging of different stimulus types within the same experimental block, thus allowing mixed-trial analysis (such as Successful and Failed inhibitions in the Go/NoGo signal). Moreover, ERPs can provide unique temporal information concerning the timing and order of activations of normal and abnormal neural activity within the block during the unfolding of cognitive tasks which can be the only significant information that differentiate between those activities. Finally EEG methodology is less invasive, less costly, and cumbersome than PET and fMRI methodology.

ERPs consist of an ordered sequence of waveforms such as P100, N100, P200, N200, P300, N400 depending on their latency and their polarity. Early components (P100 and N100 etc.) are called exogenous, because they require a stimulus, and reflect activity in primary or secondary sensory areas. However, such early ERP waves can be modulated by sustained attention and top-down cognitive control processes. Longer latency components (P300, N400 etc.) are called endogenous, because they can be present even in response to an expected missing stimulus. P300 is elicited in visual or auditory oddball tasks in response to task-relevant, salient infrequent targets, with greater amplitude over the posterior (parietal) scalp. Another waveform of interest is the N200, a prominent N200 with a frontal distribution is observed in response to NoGo stimuli in Go/NoGo tasks, and it is thought to reflect response inhibition processes. In contrast, Go stimuli elicit the parietally distributed P300.

Although spatial resolution of the ERP method is coarse, it is improved by the use of high-density and new active amplifiers sensor arrays.

Brain Network Activation (BNA) technology uses high density EEG to collect ERP data for generation of a reference brain network model (RBNM) based on common neural activations, or event-pairs, defined as any two salient electrophysiological events, each at a given scalp location, frequency band and time range, with a specific temporal relationship. The algorithm produces a visual display of BNA network patterns that is simpler to interpret than traditional EEG output, while providing information on cortical connectivity. In addition, a RBNM similarity index (BNA score) is calculated for the EEG components of time (relative and absolute), amplitude, and overall pattern (connectivity) providing objective and easily interpretable results.

The present study aims at clarifying dynamic spatio-temporal aspects of brain functional organization (e.g. inhibitory control, working memory) in MDD and cognitive dysfunction associated with MDD using BNA during the performance of the different tasks.

Recent studies have validated the use of brain network activation (BNA) analysis using ERPs to diagnose and predict treatment response in attention deficit hyperactivity disorder (ADHD), models of schizophrenia and Alzheimer's disease, concussion, pain and fibromyalgia (data on file, EIMindA).

We hypothesize that the application of BNA using ERPs may be used as a non-invasive tool to improve diagnosis, differential diagnosis, target-specific depression symptom domains such as cognition and monitoring treatment response in MDD with cognitive dysfunction.

Considering the compromised course of untreated depression and its well-known robust responsiveness to treatment, the development of an objective diagnostic tool to help diagnose individuals with MDD and predict treatment response can have a significant clinical and public health impact.

#### **Rationale for the Proposed Study:**

Vortioxetine has been shown to improve core depressive symptoms and improve cognitive function in adult outpatients with MDD and subjective complaints of cognitive function. This pilot study is intended to evaluate the extent to which BNA technology can provide clinically valuable information and provide information toward designing a subsequent confirmatory study that will further elucidate the effect of vortioxetine on MDD and cognitive function in this population. This exploratory study will ascertain the acute changes in core depression symptoms, cognitive function, tolerability, and safety using flexible-dose vortioxetine in adult outpatients with MDD with subjective complaints of cognitive functioning, as measured by BNA changes and standard outcome measures for depression and cognition.

Data suggest that the impact of vortioxetine on cognition in MDD may be independent of the antidepressant effect, perhaps through a centrally-mediated pathway different from that involved in the antidepressant effects. This study will investigate the effect of vortioxetine on cognitive dysfunction more broadly covering specific measures of attention, executive functioning and psychomotor speed, as well as assess its effect on core depressive symptoms, function and global change. The number of subjects treated in this study is generally accepted for exploratory studies and intended to demonstrate 1) improvement in cognition and efficacy in conventional MDD symptom domains, 2) improvement in cognition but no antidepressant efficacy in conventional MDD symptom domains, and, 3) no improvement of cognition and no antidepressant efficacy in conventional MDD symptom domains. We predict distinct patterns in brain network activity among these subgroups. This preliminary data is expected to provide greater insight into understanding the direct versus indirect antidepressant effects

of acute treatment with vortioxetine on cognition in MDD, and provide a basis for future clinical trials and applications.

## **STUDY OBJECTIVES AND OUTCOMES**

### **OBJECTIVES**

#### **Primary Objective:**

- To explore BNA changes from baseline to endpoint on 1) efficacy of core MDD symptoms and, 2) improvement of cognitive dysfunction with acute treatment of flexible dose vortioxetine in adult outpatients with MDD and subjective complaints of cognitive dysfunction.

#### **Secondary Objectives:**

- To evaluate the efficacy over eight weeks of treatment of flexible-dose vortioxetine (5-20 mg/day) on standard outcome measures for core depression symptoms
- To evaluate the changes in cognitive function from baseline to endpoint with flexible-dose vortioxetine (5-20 mg/day)
- To evaluate the changes in functionality over eight weeks of treatment with flexible-dose vortioxetine (5-20 mg/day)
- To explore baseline BNA patterns and clinical baseline features of:
  - core MDD symptoms (including severity)
  - cognitive dysfunction
  - functionality
- To explore change in BNA patterns and clinical changes on:
  - core MDD symptoms
  - cognitive function
  - functionality
  - adverse events attributed to vortioxetine (per investigator opinion)
- To explore correlations between patterns of BNA changes and evaluated changes in RDOC (Research Domain Criteria) domains and structures
- To explore differences in BNA patterns and identify potential neural pathways that may impact core depressive symptoms different from cognitive function
- To explore change in BNA patterns from baseline to after 2 weeks of treatment with vortioxetine with efficacy, using standard outcome measures of core depression symptoms at the end of acute treatment
- To strengthen the level of confidence with BNA patterns observed during the course of treatment that may allow identification of potential trends observed as a result of treatment, by having a screen and baseline BNA done prior to receiving treatment
- To obtain baseline BNA data in adult outpatients with MDD and subjective cognitive dysfunction prior to treatment that can be utilized for identification of BNA patterns associated with MDD
- To confirm the safety and tolerability of vortioxetine (5-20mg/day).

## **OUTCOMES**

### **Primary Outcome:**

The primary outcome of this study is to explore changes in BNA patterns from baseline to endpoint with 1) antidepressant response status; response defined as  $\geq 50\%$  change in total MADRS score from baseline to endpoint and, 2) change in cognitive function defined as change from baseline to endpoint on change in total number of correct symbols on the DSST .

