## **STATISTICAL ANALYSES**

### **Primary Efficacy Analysis**

The primary endpoint is the change from Baseline in the MADRS and DSST score. The primary endpoint will be analyzed using analysis of covariance (ANCOVA), with treatment and center as fixed factors, and baseline score as covariate. The p-values, least squares (LS) treatment means, difference between the LS treatment means, and 95% CIs for the treatment differences will be displayed.

This is a pilot study that is intended to evaluate the extent of to which BNA technology can provide clinically valuable information, and to provide data that will help design a future confirmatory study. Because this is an exploratory study, no formal sample size calculation was performed; rather, sample size has been based on that which is generally accepted by the medical community for a study of this nature. In order to strengthen the level of confidence of the results, the BNA test is performed twice before the subject is given medication to provide repeatability and two additional times during the course of treatment to allow the identification of any potential trend that may occur as a result of treatment.

The relationship between changes in BNA and BNA total mean change from baseline and endpoint will be analyzed. Changes in BNA from baseline will also be analyzed by groups defined on endpoint status (e.g. response to MADRS, remission, change in DSST).

Statistical analysis should also consider the fact that changes in brain networks may be independent of symptoms or neurocognitive scores; thus, the analysis of BNA changes across treatment duration should be also performed independently. In other words, it is possible that BNA conveys information that is not found in other methods; trying to find correlations may limit the correct interpretation. Therefore, robust trends found in BNA scores should be further researched, regardless of finding correlations to symptoms or neurocognitive tests. For example, it could be that a change in BNA, without a significant change in symptoms, means that if the treatment will be continued for a few more weeks, a delayed improvement will be found; etc.

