### **Secondary Efficacy Analyses**

Change from Baseline in TMT A, TMT B, , PDQ, MGH-CPFQ, UPSA, percentage of productivity loss (WLQ), MADRS, CGI-S, and CGI-I will be analyzed at all time points (where rated) using ANCOVA model similar to the one described above for the primary endpoints.

MADRS responders (defined as a >50% decrease from Baseline), MADRS remission (defined as a MADRS total score <10). CGI-S remission (CGT-S2), and CGI-I response (CGI-I2) will be analyzed at all time points by logistic regression, adjusting for baseline score and treatment.

Proportion of cognitive dysfunction improvement that is not due to an improvement in depressive symptoms will be analyzed using a path analysis with change from Baseline in DSST score and change from Baseline in MADRS total score as endogenous variables.

C-SSRS will be summarized at all time points using descriptive techniques.

All statistical tests will be 2-sided and at the 5% level of significance. Ninety-five percent confidence limits will be presented together with the p-values.

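### The primary BNA–mood association rests on a yes/no MADRS response; baseline-adjusted MADRS change would test it more sensitively in the same 40 subjects

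*Combined protocol and SAP*

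**What the plan says.** The Primary Outcome section has two halves. The mood half is to "explore changes in BNA patterns from baseline to endpoint with 1) antidepressant response status", with response set at a 50% threshold for "change in total MADRS score from baseline to endpoint and, 2) change in cognitive function". The cognitive half is worded as a score, "change in total number of correct symbols on the DSST".

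The Primary Efficacy Analysis section contains two further statements. One reads "The primary endpoint is the change from Baseline in the MADRS and DSST score". That endpoint is continuous and is analysed by ANCOVA, but the model has no BNA term. The other concerns BNA: "Changes in BNA from baseline will also be analyzed by groups defined on endpoint status (e.g. response to MADRS, remission, change in DSST").

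Under Secondary Outcomes, item 2a relates BNA change to the HDRS-17, HDRS-28 and QIDS-SR-16 totals, but lists MADRS only as response, remission and asymptomatic remission. The MADRS total score appears against BNA in item 3a(i), which concerns prediction of clinical outcome.

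On size, the plan has "40 subjects enrolled" and says "no formal sample size calculation was performed". On testing, "All statistical tests will be 2-sided and at the 5% level of significance".

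**The concern.** The primary objective asks how BNA change goes with change in mood and change in cognition. A responder split answers the mood part coarsely. Subjects who improve by 5% and by 49% count as the same, while subjects at 49% and 51% count as opposites. The plan's own Outcome Definitions draw a finer line, separating less than 25% change (non-response) from 25–49% (inadequate response); the primary dichotomy merges the two.

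Nothing in the data forces this choice. MADRS runs from 0 to 60 and is scheduled at every visit in Appendix I. The BNA Analysis section gives each subject an individual BNA change score. With 40 subjects before any dropout, a real but moderate association could be missed in a pilot meant to guide a confirmatory study.

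A second consequence is possible. If DSST change stays continuous, as the Primary Outcome words it, the mood half is tested less sensitively than the cognitive half.

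**Working it through.** The documents state no power, effect size, response rate or expected dropout, so there is no figure of theirs to reproduce.

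**Inputs from the documents.** N = 40 (Number of Subjects); two-sided 5% tests (Secondary Efficacy Analyses); a binary mood variable (Primary Outcome); an individual BNA change score (BNA Analysis).

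**Assumptions.** MADRS change is roughly normal. Its relation to one scalar BNA change score is linear. The response rate p is 30–70%, with 20–80% as a wider range. The number evaluable is 40, or 32 if a fifth lack an endpoint.

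**Information kept after the split.** Relative efficiency = φ(z)² / [p(1−p)], where z is the standard normal quantile at p and φ the normal density.

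- p = 0.5: φ = 0.3989, and 0.1592 / 0.25 = 0.637
- p = 0.3 or 0.7: φ = 0.3477, and 0.1209 / 0.21 = 0.576
- p = 0.2 or 0.8: φ = 0.2800, and 0.0784 / 0.16 = 0.490

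| Response rate | Kept | Lost | Equivalent N of 40 |
|---|---|---|---|
| 50% | 63.7% | 36.3% | 25.5 |
| 40% or 60% | 62.2% | 37.8% | 24.9 |
| 30% or 70% | 57.6% | 42.4% | 23.0 |
| 20% or 80% | 49.0% | 51.0% | 19.6 |

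The loss is smallest at 50%, so under these assumptions it cannot fall below 36%.

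**Detectable correlation at 80% power.** With the continuous score, r = tanh[(1.960 + 0.842)/√(N−3)]. For N = 40 this is tanh(2.802/6.083) = 0.43. The split shrinks the correlation by the square root of the efficiency (0.798 at p = 0.5; 0.759 at p = 0.3 or 0.7). The underlying correlation must then be 0.4306/0.798 = 0.54 to 0.4306/0.759 = 0.57. For N = 32 the figures are 0.48 continuous against 0.60–0.63 binary.

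**Simulated power** (20,000 trials per setting, N = 40, response rates of 30%, 50% and 70%):

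| True correlation | Continuous | Yes/no response |
|---|---|---|
| 0.3 | 47–48% | 29–32% |
| 0.4 | 74–75% | 49–54% |
| 0.5 | 92–93% | 70–75% |

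**How DSST is handled.** The Primary Outcome words it as a change in score. The Primary Efficacy Analysis lists DSST change among the variables that define groups. Secondary outcome 4 groups subjects on DSST improvement, and item 5d uses a 70% improvement cut-off. No section commits to a continuous model of BNA against DSST change.

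**The case against.** The strongest case for leaving the plan alone has four parts.

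**Responder groups fit the question.** The Rationale predicts distinct BNA patterns in subgroups defined by antidepressant efficacy and cognitive improvement, and the BNA algorithm builds group networks. This stands as a reason to keep the responder contrast. It does not require that contrast to carry the primary association, since an individual change score exists.

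**Continuous mood scores are already set against BNA.** A reader might infer that the plan throws away continuous mood information. The documents do not support that: item 2a includes the HDRS-17, HDRS-28 and QIDS-SR-16 totals, and item 3a(i) includes the MADRS total. What remains is narrower: which analysis is labelled primary, and the absence of the MADRS total from item 2a.

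**The mood–cognition imbalance is not established.** A reader might infer that the design will make BNA look more related to cognition than to mood. That follows only if DSST stays continuous. Because the Primary Efficacy Analysis lists DSST change as a grouping variable, both halves may be coarsened.

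**The size is assumed, and no power claim is breached.** This is an exploratory pilot. BNA yields several scores (timing, amplitude, overall pattern) and similarity indices to each group network, so a single-correlation calculation only approximates the planned work. This stands, and it makes the point one of efficiency rather than a numerical error.

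**Conclusion.** The point holds in a limited form. The designated primary BNA–mood association uses a binary MADRS response where a continuous score is available for the same subjects. Under approximate normality, a linear relation with a scalar BNA change score and a 30–70% response rate, the split costs about 36–42% of the information for that association. The cost is at least 36% at any response rate and about 51% at 20% or 80%. The formula is firm; the response rate and distribution are assumptions, not figures from the plan.

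The loss does not extend to the study as a whole. Unequal sensitivity between the mood and cognitive halves is a possible harm that depends on how DSST is finally analysed. The change is worth making because it gains precision at almost no cost in a small study.

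**What to change.** In Primary Outcome part 1, Secondary Outcomes item 2a and the Primary Efficacy Analysis:

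- Make the primary mood variable the change in MADRS total from baseline (Visit 2) to endpoint, with endpoint defined as Visit 10 or early termination. The Synopsis and the Visits 2–10 section already take an endpoint BNA at early termination, so a Visit 10-only rule would drop those subjects.
- Relate it to individual BNA change by regression or partial correlation, adjusted for baseline MADRS. The adjustment matters because response is a percentage cut and so depends on the starting score.
- State that DSST change is likewise analysed as continuous, using its scheduled pre-treatment value. Appendix I marks DSST only at Screen and Visit 10 or early termination, so its baseline is not the same visit as that of MADRS. The exclusion criteria refer to a DSST score at the Baseline Visit, and the two passages must be reconciled.
- Keep 50% response and the remission groups as supportive analyses, with one definition of response. The Primary Outcome speaks of a change of at least 50%, Outcome Definitions of a decrease of at least 50%, and Secondary Efficacy Analyses of a decrease of more than 50%.

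The cost is wording; no new data are needed. The downside is that the clinically familiar responder contrast becomes supportive.
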